2.0 OBJECTIVES

2.1 Primary Objective

Demonstrate that surface guided, breath-hold respiratory gated delivery of CT-guided stereotactic adaptive radiotherapy (CT-STAR) is feasible in the abdomen and lower thorax by confirming that gated treatment can be delivered successfully in more than 75% of scheduled treatment fractions using a novel surface guidance system. Success will be defined as delivery of a given treatment fraction in one on-table attempt, without requiring use of a secondary (backup) motion management system, or alternative treatment machine. Unsuccessful delivery of a fraction will be defined as multiple attempts for gating without reproducible positioning, breath-hold, and/or surface guidance feedback, such that the fraction is abandoned.

2.2 Exploratory Objectives

1. Determine geometric agreement between breath-hold positioning as determined by a novel surface guidance system vs. concomitant breath-hold CBCT image sets.
2. Evaluate the compatibility of a standard-of-care respiratory gating system and the novel surface-guidance system for concomitant use.
3. Determine the minimum safe planning target volume and planning organ-at-risk volumes to be subsequently utilized with the novel surface guidance system.
4. Determine the local, in-field control rate at three months post-treatment.
5. Determine acute toxicity rates at three months post-treatment.
6. Identify patient and or treatment factors that maximize the potential efficacy of surface guided breath-hold respiratory gating, such as differences in surface topography and skin tone.

3.0 PATIENT SELECTION

3.1 Inclusion Criteria

1. Primary or metastatic disease of the abdomen or lower thorax, with biopsy-proven or radiographically diagnosed disease histology of solid tumor categorization, with the exception of small cell cancers.

2. Must be medically fit for SBRT as determined by the treating physician, with at least one disease site to be deemed suitable for treatment with CT-guided stereotactic radiation to the abdomen or thorax as per radiation oncologist evaluation.
3. At least 18 years of age.
4. Karnofsky performance status > 60 (see Appendix A)
5. Capable of single deep inspiratory breath-hold or end-exhale breath-hold of at least 17 seconds in duration and of repeated end-exhale or deep inspiratory breath-hold of at least 10 seconds in duration upon verbal instruction.
6. Must have completed any systemic therapy at least one week prior to planned start of SBRT (two weeks preferred), and must have no plans to initiate systemic therapy for at least one week following end of SBRT (two weeks preferred).
7. Able to understand and willing to sign an IRB approved written informed consent document (or that of legally authorized representative, if applicable).

3.2 Exclusion Criteria

1. Past history of radiotherapy within the projected treatment field of any of the disease sites to be treated by CT-guided SBRT.
2. Currently receiving any investigational agents.
3. Uncontrolled intercurrent illness including, but not limited to, ongoing or active infection, symptomatic congestive heart failure, unstable angina pectoris, cardiac arrhythmia, or psychiatric illness/social situations that would limit compliance with study requirements.
4. Pregnant and/or breastfeeding. Patient must have a negative pregnancy test within 14 days of study entry.

3.3 Inclusion of Women and Minorities

Both men and women and members of all races and ethnic groups are eligible for this trial.

4.0 REGISTRATION PROCEDURES

Patients must not start any protocol intervention prior to registration through the Siteman Cancer Center.

The following steps must be taken before registering patients to this study:

1. Confirmation of patient eligibility
2. Registration of patient in the Siteman Cancer Center OnCore database
3. Assignment of unique patient number (UPN)

4.1 Confirmation of Patient Eligibility

Confirm patient eligibility by collecting the information listed:

1. Registering MD's name
2. Patient's race, sex, and DOB
3. Three letters (or two letters and a dash) for the patient's initials
4. Copy of signed consent form
5. Completed eligibility checklist, signed and dated by a member of the study team
6. Copy of appropriate source documentation confirming patient eligibility

4.2 Patient Registration in the Siteman Cancer Center OnCore Database

All patients must be registered through the Siteman Cancer Center OnCore database.

4.3 Assignment of UPN

Each patient will be identified with a unique patient number (UPN) for this study. All data will be recorded with this identification number on the appropriate CRFs.

4.4 Screen Failures

Screen failures are defined as participants who consent to participate in the clinical trial but are not subsequently entered in the study. A minimal set of screen failure information is required to ensure transparent reporting of screen failure participants, to meet the Consolidated Standards of Reporting Trials (CONSORT) publishing requirements and to respond to queries from regulatory authorities. Minimal information includes demography, screen failure details, eligibility criteria, and any serious adverse event (if applicable).

5.0 TREATMENT PLAN AND DELIVERY

5.1 Radiation Therapy Guidelines

5.1.1 Dose, Fractionation

Radiotherapy will consist of stereotactic body therapy, to be given over five fractions, delivered once daily or once every other day for a period of one to two weeks, for a total of five treatments. Of note, safety of treatment will be kept within established guidelines based on standard institutional constraints applied to normal

tissues. Patients will be planned for a minimum dose of 35 Gy in five fractions to the PTV, with optional dose adaptation based on safety constraints that are already approved of, up to a maximum allowed total dose of 60 Gy in five fractions to the PTV. The maximum allowable prescription dose to the PTV on any day with adaptive planning will be constrained to 12 Gy, subject to coverage goals below.

5.1.2 Simulation Procedures/Patient Positioning

All patients will undergo both CT and CBCT simulation in positioning appropriate for the specific treatment site. When medically feasible and applicable, patients will be simulated with IV and small bowel contrast (for non-thorax cases).

5.1.3 Clinical Target Volume (CTV) and Planning Target Volume (PTV) Definitions

The treatment target will be defined based on the gross tumor volume (GTV) only. No CTV expansion will be utilized, as per standard-of-care procedures in the setting of SBRT. Additionally, no ITV expansion will be utilized, as gated delivery is planned. The PTV will be generated at the discretion of the treating physician but should range between 3 mm and 7 mm.

5.1.4 Initial Treatment Planning

All patients will be initially planned to at least 35 Gy in 5 fractions, subject to hard constraints based on the treatment site. Dose volume histogram (DVH) information for the target volumes and surrounding critical structures is mandatory. This is to assist in interpreting outcome, including morbidity. Coverage goal will be for 95% of the volume to be covered by 95% of the dose, although in situations where a critical structure is violated, reduction of dose will be allowed in areas of overlap.

5.1.5 SBRT Dose Constraints

Standard institutional 5-fraction organ-at-risk dose constraints will be used, at the discretion of the treating physician, and in concordance with the treated (abdomen vs. thorax) site. For those patients undergoing optional plan adaptation, on treatment days where all constraints are met, the prescription dose for that day's treatment may be escalated up to a maximum dose of 12 Gy, if all constraints are met. Adaptive plans will be evaluated under the assumption that the delivered adaptive plan would meet all hard constraints for 5 fractions with stable anatomy. For example, on a given day, the maximum cord dose (to 0.5cc) will be 5 Gy (extrapolate to maximum dose 25 Gy over 5 fractions).

5.1.6 Adaptive Treatment Planning

When patients present for their first SBRT treatment session, patients planned for optional adaptation will be evaluated by the treating physician to determine if

adaptive planning is indicated. Treatment plan re-optimization will be performed for dose adaptation if it is determined that the patient's anatomy allows for dose adaptation with acceptable sparing of normal structures (i.e., not violating the predetermined hard constraints based on safety constraints that are already approved of for routine, clinical use). Dose adaptation can also be done in cases where on the volumetric imaging attained, there is noted to be violation of previously met hard constraints. If there are no violations of any hard constraint, the maximum dose delivered will be capped at 12 Gy per treatment fraction.

5.1.7 Quality Assurance of Adaptive Plans

Patient specific QA will be performed at each fraction prior to delivery of the adaptive treatment plan for any patients undergoing optional dose adaptation. Given that dose measurements will not be possible with the patient on the table, this will be achieved by performing an independent secondary QA check using Mobius. The independent QA will be compared to the dose distribution exported from the ETHOS system, looking at dose volume histograms and 3D gamma analysis of all voxels within the patient. After completion of the automated checks, a final review by physics will be required prior to proceeding to treatment delivery.

5.1.8 Surface-Guided Gated Delivery

At time of CT and CBCT simulation, a baseline reference surface region of interest will be determined. The region of interest (ROI) will be selected on an individual basis for the most sensitivity to detect respiratory motion. At time of first treatment, the patient will be set up to marks and the reference surface. Breath-hold CBCT daily alignment image will be acquired and a new reference surface ROI will be established based on the daily anatomy. The reference surface will be monitored using the Identify system and a respiratory trace will be generated and displayed to the treatment team for breath-hold respiratory gating of treatment delivery. A visual feedback system will be displayed to the patient to aid in respiratory coaching for breath-hold. After treatment alignment and optional adaptation, a repeat breath-hold CBCT will be obtained to evaluate for any patient motion. Shifts can be applied as needed prior to initiation of delivery. CBCT can be repeated in the breath-hold position at set time points, e.g., after each arc in VMAT plans, and at the end of treatment delivery. A recommended maximum of 10 images will be taken per fraction. This will be used for intrafraction patient monitoring as well as subsequent evaluation of concordance between geometric patient position as identified by the Identify system vs. CBCT.

5.2 Evaluability Guidelines

All patients who receive any radiation therapy are evaluable for the primary objective (feasibility of delivering CT-guided SBRT with surface-guidance for gated delivery).

Patients who receive at least one fraction of radiation therapy are evaluable for the

exploratory objectives relating to tumor response/control rate and toxicity.

Success will be defined as delivery of a given treatment fraction in one on-table attempt, without requiring use of a secondary (backup) motion management system, or alternative treatment machine. Unsuccessful delivery of a fraction will be defined as multiple attempts for gating without reproducible positioning, breath-hold, and/or surface guidance feedback, such that the fraction is abandoned.

Should respiratory gating using the Identify optical surface guidance system not be feasible for any given fraction or patient, the treatment fraction will be delivered using an alternative, backup motion management device and/or an alternative linear accelerator as per standard-of-care therapy.

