	
 2. Evaluate the compatibility of a standard-of-care respiratory gating system and the novel surface-guidance system for concomitant use. 3. Determine the minimum safe planning target volume and planning organ-at-risk volumes to be subsequently utilized with the novel surface guidance system. 4. Determine the local, in-field control rate at three months post-treatment. 5. Determine acute toxicity rates at three months post-treatment. 6. Identify patient and or treatment factors that maximize the potential efficacy of surface guided breath-hold respiratory gating.
Endpoints:	
Primary Endpoint: Percentage of scheduled treatment fractions delivered successfully using the surface guidance system. Success will be defined as delivery of a given treatment fraction in one on-table attempt, without requiring use of a secondary (backup) motion management system, or alternative treatment machine. Unsuccessful delivery of a fraction will be defined as multiple attempts for gating without reproducible positioning, breath-hold, and/or surface guidance feedback, such that the fraction is abandoned.
 
Exploratory Endpoints:
 
 1. Geometric agreement between breath-hold positioning as determined by a novel surface guidance system compared with standard of care concomitant breath-hold CBCT image sets, as evaluated by average symmetric surface distance (ASSD), modified Hausdorff distance (MHD), and Dice similarity coefficient measurements. 2. Qualitative evaluation of the compatibility of a standard-of-care respiratory gating system and the novel surface-guidance system for concomitant use. 3. Quantitative and qualitative measurement of minimum planning target volume (PTV) margins and planning organ-at-risk volumes to be subsequently utilized with the novel surface guidance system as determined through measurement evaluations in exploratory endpoint 1. 4. Local, in-field control rate at three months post-treatment will be determined as part of standard-of-care clinical evaluation by the treating physicians, using RECIST criteria. 5. Qualitative description of acute (within 90 days) Grade 3 or higher non-hematologic toxicity events related to radiation therapy at three months post-treatment. 6. Qualitative description of patient and treatment site factors, such as unique patient surface topography or skin tone, that

	might impact surface imaging tracking at the region of interest.

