11.2 Sample Size

The primary endpoint of this study is to assess the feasibility of surface-guided, respiratory gated delivery of CT-guided stereotactic radiotherapy for upper abdomen and lower thorax malignancies by confirming that gated treatment can be delivered successfully in more than 75% of scheduled treatment fractions using a novel surface guidance system. A total of 10 evaluable patients (as defined in Section 5.2) will be included, with five treatment fractions each, for a total of $n = 50$ evaluable fractions. In order to assess the feasibility of the gating methodology on the novel surface guidance system, we conducted a one-sample reliability demonstration test based on the binomial distribution. The study will be powered based on an expected success rate of 95% and a minimum accepted rate of 75%. With 10 patients and 5 fractions per patient, 50 total fractions ($n=50$) would be assessed. In-patient correlation is anticipated, as surface-guided delivery is in part patient-surface dependent, with an anticipated value of 0.2. With a one-sided alpha of 0.25 and $n=50$ fractions across 10 unique patients, we would have a minimum of 92% power to detect feasibility of successful gated delivery.

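### Does the narrow definition of an unsuccessful fraction bias the primary feasibility rate upward?

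*Combined protocol and SAP*

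**What the plan says.** The Protocol Summary gives the primary endpoint as "Percentage of scheduled treatment fractions delivered successfully using the surface guidance system". Sections 2.1, 11.2 and 11.3 keep the same form: successful deliveries as a share of scheduled fractions, to exceed 75%.

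Two definitions accompany the endpoint in the Protocol Summary and in Sections 2.1, 5.2 and 11.3. The first: "Success will be defined as delivery of a given treatment fraction in one on-table attempt", with no backup motion management system and no other treatment machine. The second labels a fraction unsuccessful when there are "multiple attempts for gating without reproducible positioning, breath-hold, and/or surface guidance feedback, such that the fraction is abandoned".

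Section 5.2 also provides a route to backup: "Should respiratory gating using the Identify optical surface guidance system not be feasible for any given fraction or patient", the fraction is given with another device or linear accelerator. It sets no minimum number of gating attempts first. Evaluability is defined for patients: "All patients who receive any radiation therapy are evaluable for the primary objective".

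Section 11.2 fixes the count: "A total of 10 evaluable patients (as defined in Section 5.2) will be included, with five treatment fractions each", hence 50 fractions. It states both design rates as success rates, an "expected success rate of 95% and a minimum accepted rate of 75" per cent, with one-sided alpha 0.25, within-patient correlation 0.2 and power of at least 92%. Section 11.5 adds no scoring rule.

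**The concern.** The second definition needs both repeated gating attempts and abandonment, so it covers less than everything that is not a success. Two kinds of fraction meet neither definition:

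- a fraction delivered under surface guidance at a second on-table attempt, which fails the one-attempt test but was not abandoned;
- a fraction moved to backup after one gating attempt or none, which cannot be a success but lacks the multiple attempts.

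The second kind is foreseeable, because Section 5.2 allows the move for a single fraction or a whole patient. No sentence says that every fraction that is not a success is a failure.

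If staff scored failures by the narrower label, or dropped fractions that meet neither as not evaluable, the rate would go up or stay the same and never go down. Feasibility is the only primary endpoint and rests on ten patients, so a few reclassified fractions could decide the result when the true rate is near the 75% minimum.

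**Working it through.** **Inputs from Section 11.2.** 10 patients × 5 fractions = 50; minimum rate 0.75; expected rate 0.95; one-sided alpha 0.25; within-patient correlation 0.2. The documents do not say how non-successes divide between abandoned fractions and fractions meeting neither label, so that share, g, is an assumption.

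**The plan's own power figure.** Correlation is modelled as ten beta-binomial patients of five fractions each. The cut-off is the smallest count with tail probability at most 0.25 when the rate is 0.75.

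| Count | Independent fractions | Correlation 0.2 |
|---|---|---|
| P(X ≥ 40), rate 0.75 | 0.262 | 0.329 |
| P(X ≥ 41), rate 0.75 | 0.164 | 0.242 |
| P(X ≥ 41), rate 0.95 | 0.9998 | 0.995 |

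The cut-off is 41 of 50 either way. Power is 99.5% with correlation 0.2. This does not reproduce 92%, but it is consistent with a stated minimum of 92%. The present question does not depend on that figure.

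**What a departure from the endpoint would do.** Let S be successes, F fractions meeting the unsuccessful definition and U fractions meeting neither, with S + F + U = 50.

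- Endpoint as written: S/50.
- Failures counted by the narrow label: 1 − F/50 = (S + U)/50.
- Fractions meeting neither dropped: S/(S + F).

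With assumed counts S = 36, F = 6, U = 8, these give 36/50 = 72.0%, 44/50 = 88.0% and 36/42 = 85.7%. The first is below 75% and the other two are above it.

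With a true success rate of 75%, the narrow label would show a rate of 0.75 + 0.25g:

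| Assumed g | Apparent rate | P(≥ 41), independent | P(≥ 41), correlation 0.2 |
|---|---|---|---|
| 0 | 75.0% | 16% | 24% |
| 0.10 | 77.5% | 28% | 35% |
| 0.25 | 81.25% | 53% | 54% |
| 0.50 | 87.5% | 91% | 85% |

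Correlation 0.2 is assumed for both ways of counting.

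**Which row the plan uses.** Scoring each outcome by the endpoint in the Protocol Summary and the success definition in Section 5.2:

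| Outcome of a scheduled fraction | In numerator? | In denominator? |
|---|---|---|
| One attempt, surface guidance only | yes | yes |
| Second on-table attempt, surface guidance | no: more than one attempt | yes |
| Moved to backup or another machine | no: excluded by name | yes |
| Abandoned after repeated gating attempts | no | yes |

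The unsuccessful label is not needed to fill any cell. No section computes the rate as one minus the unsuccessful share, and none removes fractions that meet neither label. Both rates in Section 11.2 are success rates on 50 fractions. The plan as written therefore corresponds to g = 0, where the chance of passing at a true 75% is 24%, within the planned 25%.

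**The case for a change.** The best case for a change is that the protocol states a definition of unsuccessful delivery four times, so staff who classify fractions could reasonably use it. If it plays no part in scoring, the text should say so. Settling the matter after outcomes are known would leave the result open to challenge. One sentence would close the gap and would alter neither the sample size nor the power.

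The textual mismatch stands, and so does the direction: using the narrow label could not lower the rate. Two further points of wording also stand. Section 11.2 speaks of evaluable fractions although Section 5.2 defines evaluability only for patients. The term on-table attempt is not defined.

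The bias itself does not follow. It needs an analyst to set aside the stated endpoint and build a different one from the complement of a label. Fractions moved to backup are excluded from success by name. Second-attempt deliveries depend on the undefined term. Section 5.1.8 foresees repeat breath-hold CBCT and shifts within a session. If an on-table attempt means one session on the table, several gating tries that end in delivery are still one attempt, and this group shrinks mainly to fractions completed in a second session. How an attempt is read affects who counts as a success, but that is a matter of applying the success definition consistently. It does not arise from the gap between the two labels. The word evaluable in Section 11.2 changes no number, because the same section refers to scheduled fractions and fixes 50.

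**Conclusion.** No change follows. The two definitions are not complements, but the primary rate is fixed without the narrower one: successes over scheduled fractions, 50 in all. Second-attempt and backup deliveries already count against the device, so the planned estimate carries no upward bias from this source. The larger figures (54% or 85% instead of 24% at a true rate of 75%) describe a calculation the plan does not contain, with assumed shares of one quarter and one half for fractions meeting neither label. At the expected 95% rate, 99.5% of trials would reach 41 of 50 on the strict count, so the ambiguity would be harmless there in any case.

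The unsuccessful definition is best read as a description of how a fraction typically fails. A sentence making the two labels complementary would restate what the endpoint implies and leave the result the same. This conclusion rests on the analysts following the endpoint as written and applying one reading of an on-table attempt throughout.

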5.3 General Concomitant Medication and Supportive Care Guidelines

Patients are not permitted to receive systemic therapy beginning one week prior to start of SBRT and continuing through SBRT and one week post-completion of SBRT. (It is preferred that patients do not receive systemic therapy within 2 weeks of starting and ending SBRT, but that is left to the discretion of the treating physician.)

